12.1 FUNDING SOURCE27
12.2 CONFLICT OF INTEREST27
12.3 SUBJECT STIPENDS OR PAYMENTS27
13 PUBLICATION PLAN27
14 REFERENCES28

List of Abbreviations

AE	Adverse Event
CC	Cubic Centimeters
CDRS	Children's Depression Rating Scale
CFR	Code of Federal Regulations
CGI	Clinical Global Impressions
CMRR	Center for Magnetic Resonance Research
CRF	Case Report Form
CTSI	Clinical and Translational Science Institute
DSMB	Data and Safety Monitoring Board
DSMP	Data and Safety Monitoring Plan
FDA	Food and Drug Administration
GCP	Good Clinical Practice
HIPAA	Health Insurance Portability and Accountability Act of 1996
IDS	Investigational Drug Services
IRB	Institutional Review Board
KG	Kilogram
K-SADS-PL	Kiddie-Sads-Present and Lifetime
MDD	Major-Depressive Disorder
MEG	Magnetoencephalography
MG	Milligram
ML	Milliliter
MMC	Mayo Mail Code
MRI	Magnetic Resonance Imaging
MRS	Magnetic Resonance Spectroscopy
NOS	Not Otherwise Specified
PET	Positron Emission Tomography
PHA	Phytohemagglutinin
PHI	Protected Health Information
PI	Principal Investigator
SAE	Serious Adverse Event
TRD	Treatment-Resistant Depression
VA	Veterans' Affairs

CONFIDENTIAL

This material is the property of the University of Minnesota. Do not disclose or use except as authorized in writing by the study sponsor

Information Resources

	Name / Address	Phone / Fax / E-mail
Principal Investigator	[name] [name]	[contact] [contact]
Questions concerning eligibility	[name] [name]	[contact] [contact]
For patient enrollment	[name]	
Questions concerning drug ordering, Shipment, transfer or returns	[name]	
Lab shipping or requests	[name]	
Submission of data forms / Questions on data management	[name]	

Study Summary

Title	A Personalized Approach to Achieving a Sustained Response to Treatment for Adolescent Depression
Short Title	PTAD GIA
Protocol Number	1206M15365
Phase	2
Methodology	open label pilot
Study Duration	3 years
Study Center(s)	Single-center
Objectives	To develop and assess the feasibility, acceptability, and preliminary efficacy of a personalized approach to delivering continuation treatment
Number of Subjects	30
Diagnosis and Main Inclusion Criteria	Male and female adolescents (ages 12-18) will be eligible for the study if they completed acute phase treatment and showed at least a partial response to treatment (CGI-I of minimally improved or better (CGI-I \leq 3)). Adolescents will enter continuation treatment having either received 12 sessions of IPT-A, 16 sessions of IPT-A, or 12 sessions of IPT-A plus fluoxetine.
Study Product, Dose, Route, Regimen	Adolescents who received fluoxetine during the acute phase and were responders (CGI-I = much improved or very much improved (CGI-I = 1 or 2)) will continue their acute phase dosing regimen and will meet with the psychiatrist on a monthly basis. Adolescents who received fluoxetine during the acute phase and were partial responders (CGI-I = minimally improved (CGI-I = 3)) will enter the continuation phase on 40mg fluoxetine, and will have their dose increased to 60mg. Adolescents who received only IPT-A during acute phase and were partial responders (CGI-I = minimally improved (CGI-I = 3)) will begin treatment with fluoxetine, in addition to continuing their IPT-A treatment. The dosage schedule will be 10mg per day for the first week and 20mg per day for the following 5 weeks. If no treatment response is observed by the 6th week, the dosage can be increased to 40mg per day.¹⁵
Duration of administration	16 weeks
Reference therapy	Interpersonal Psychotherapy for Depressed Adolescents (IPT-A)

CONFIDENTIAL

This material is the property of the University of Minnesota. Do not disclose or use except as authorized in writing by the study sponsor

Statistical Methodology	

1. Mean [95% confidence interval] treatment satisfaction for each adaptive treatment strategy (ATS)
2. Mean therapy session attendance and dropout rates for each ATS.
3. Within-subject change scores in CDRS-R, SAS-SR, and CGAS scores for the early and late decision point groups from pre- to post-treatment using repeated measures ANOVA.
----------------------------	--

CONFIDENTIAL

1 Introduction

This document is a protocol for a human research study. This study is to be conducted according to US and international standards of Good Clinical Practice (FDA Title 21 part 312 or 812 and International Conference on Harmonization guidelines), applicable government regulations and Institutional research policies and procedures.

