possible that adolescents seeking treatment from a community clinic might be at a greater risk for clinical deterioration and might be less likely to demonstrate a clinical improvement than if they received the treatments provided in this study. What is experimental in this study is the criteria for initiating a change in the treatment plan, the timing of a potential change in the treatment plan, and the type of change to the treatment plan. Currently, there are virtually no empirically-derived guidelines to direct clinicians in deciding whether, when, or how to alter a treatment plan for adolescent depression. Consequently, we expect the relation of the anticipated benefits to the risks to be at least as favorable to the subjects as that presented by available non-study treatment.

2 Study Objectives

Aim 1: Assess the feasibility and acceptability of the personalized continuation treatment strategy.

- Hypothesis 1: Adolescents who responded to the acute phase treatment provided in the K23 study and their parents will consent to participate in continuation treatment.
- Hypothesis 2: Adolescents will be adherent to continuation treatment and will complete the continuation treatment protocol.
- Hypothesis 3: Adolescents and parents will report satisfaction with continuation treatment.
- Hypothesis 4: Treating clinicians will report satisfaction with continuation treatment.

Aim 2: Estimate variances of primary and secondary outcomes with the continuation treatment.

- Hypothesis 5: Adolescents who were responders to acute treatment will show sustained response to continuation treatment.
- Hypothesis 6: Adolescents who were partial responders to acute treatment will show significant improvement in depressive symptoms and social and global functioning.

Aim 3: Conduct exploratory hypothesis-generating analyses to inform further development of the personalized continuation treatment strategy to be tested in a subsequent R01 proposal.

3 Study Design

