5.3 Method for Assigning Subjects to Treatment Groups

There is no randomization in this study. Assignment to treatment groups is described above (based on CGI-I score).

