- Hypotheses 5 & 6: (1) Primary analyses will examine within-subject change scores in CDRS, C-SSRS and CGAS over the course of acute and continuation treatment using repeated measures analysis of variance (ANOVA). Linear regression and analysis of covariance (ANCOVA) adjusting for pre-treatment scores will also be used to analyze changes in adolescents' outcomes. The magnitudes of changes in outcomes variables over time will be assessed using the paired t-test or Wilcoxon signed-rank test for continuous variables. Mixed-effects regression models will also be employed to compare CDRS, C-SSRS, and CGAS scores over multiple time points in order to obtain information on specific patterns of change over time. (2) Secondary analyses comparing within-subjects change scores across treatment groups on self-report measures of depression (BDI-II) and functioning (CBQ, SAS-SR) will be conducted using two-sample t-test, Wilcoxon rank sum test, and linear regression analysis. Hierarchical linear modeling (HLM) will also be conducted to compare scores over multiple time points within each treatment group. (3) Recovery will be defined as an absence of depression symptoms on the KSADS-PL for at least 8 weeks. Relapse will be defined as the reemergence of 5 or more symptoms of depression on the KSADS-PL. The percentage of adolescents who meet recovery criteria, and associated 95% confidence interval will be calculated. The percentage of adolescents who meet relapse criteria, and associated 95% confidence interval will be calculated. For those with a relapse, the mean (SD) time from recovery to relapse will be calculated.

Exploratory Analyses: Exploratory analyses will be conducted to determine whether comorbid psychiatric disorders, baseline severity of depression, and different forms of functioning (CBQ, SAS-SR, CGAS) predict or moderate positive or negative treatment outcomes. Potential predictors and moderators will be used to refine the personalized treatment strategy that will be tested in the subsequent R01.

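### The main clinical-change analysis is not planned by responder status: the synopsis uses an undefined grouping, section 7.2 part 1 states none, and the two differ on outcomes and time window

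*Combined protocol and SAP*

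**What the plan says.** The Study Summary (Statistical Methodology, item 3) plans to analyse "Within-subject change scores in CDRS-R, SAS-SR, and CGAS scores" for the "early and late decision point groups" "from pre- to post-treatment using repeated measures ANOVA".

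Section 7.2, under Hypotheses 5 and 6, has three parts. Part 1, called the primary analyses, examines "within-subject change scores in CDRS, C-SSRS and CGAS over the course of acute and continuation treatment" by repeated measures ANOVA, with ANCOVA, paired tests and mixed models in support. Part 2 puts the SAS-SR among the secondary self-report measures, compared across treatment groups. Part 3 gives recovery and relapse percentages with 95% confidence intervals.

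Section 5.3 says "There is no randomization in this study" and "Assignment to treatment groups is described above (based on CGI-I score"). Hypothesis 5 in section 2 reads "Adolescents who were responders to acute treatment will show sustained response to continuation treatment". Hypothesis 6 expects partial responders to improve in depressive symptoms and in both social and global functioning. Section 3.3 lists the CDRS, C-GAS, SAS-SR and CGI response status as secondary endpoints. Section 3.4 lists the C-SSRS among the primary safety endpoints. Section 4.1 admits only adolescents with CGI-I of 3 or less after acute treatment.

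**The concern.** An analyst holding only this protocol cannot place a subject in either synopsis group. Turning to section 7.2 part 1 does not fully solve the problem, because that part names no groups at all.

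The two hypotheses expect different things: stability in responders and improvement in partial responders. A single pooled estimate of change answers neither. The two statements also name different outcomes and different time windows, which leaves room to choose after the data are seen. Aim 2 is to estimate outcome variances, and the results are meant to inform a later R01 proposal. It should therefore be clear which population, scale and period each estimate describes.

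**Working it through.** The documents give no alpha, power, standard deviation or group split behind the sample of 30, so there is no plan figure to reproduce. The check is a side-by-side reading.

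| Element | Synopsis item 3 | Section 7.2 part 1 | Elsewhere in the protocol |
|---|---|---|---|
| Groups | Decision-point groups, undefined | None stated | Responders and partial responders by CGI-I (sections 2, 3.1, 5.3) |
| Outcomes | CDRS-R, SAS-SR, CGAS | CDRS, C-SSRS, CGAS | CDRS, C-GAS, SAS-SR in 3.3; C-SSRS in 3.4 |
| Window | Before to after treatment, with no statement of which phase | Acute plus continuation | Continuation entry at week 16, assessments at weeks 24 and 32 (3.1) |

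**Groups.** The nearest candidate for an inherited grouping is the set of acute histories in section 4.3: 12 sessions of IPT-A, 16 sessions, or 12 sessions plus fluoxetine. None is labelled early or late, and three histories do not reduce to two groups without a rule. Section 1.1 describes the linked acute study but gives no early or late decision time.

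**Outcomes.** Reading CDRS and CDRS-R as the same scale, two of the three measures agree. The SAS-SR and C-SSRS are exchanged. On this point section 7.2 part 1 is the outlier: the synopsis agrees with section 3.3, and part 1 contains no dedicated social functioning scale although Hypothesis 6 names that domain.

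**Pooling.** Let p be the share of responders, with mean continuation-phase changes D_R in responders and D_PR in partial responders. The pooled mean change is

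pooled = p × D_R + (1 − p) × D_PR.

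If Hypothesis 5 holds in the sense that D_R = 0, the pooled value is (1 − p) × D_PR, which understates the change in partial responders. The documents do not give p. Assuming an even split of 15 and 15, the pooled value is half of D_PR. At the same split, responders worsening by d and partial responders improving by d would give a pooled change of zero.

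**Window.** Change over both phases is D_acute + D_continuation. Everyone enrolled was rated at least minimally improved over the acute phase. The CGI-I is not the CDRS-R or C-GAS, but it rates improvement in the same illness, so D_acute can be expected to lean towards improvement through selection. The sum can then show improvement even if D_continuation is zero. The period from week 16 to week 32 isolates the treatment under study.

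**The case against.** The strongest reply is that section 7.2, not a line in the summary, is the operative plan, and it works. Its within-subject, paired and mixed-model analyses need no decision-point factor. The SAS-SR is not lost, since part 2 analyses it, and part 2 compares treatment groups, which section 5.3 ties to CGI-I score. Relapse in part 3 bears directly on sustained response. The mixed models over several time points could also yield a continuation-phase contrast. All of this stands. A reader might infer that the clinical analysis cannot be run, or that Hypotheses 5 and 6 have no analysis. The documents do not support either reading: only the grouping in synopsis item 3 is unusable as written.

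Nor is it certain that the grouping has no source. All subjects come from the linked acute study, section 1.4 calls the timing of a treatment change experimental, and the figure in section 3.1 is not shown. The surviving legend names only responder, partial responder and nonresponder, so a definition inside the figure is unlikely but cannot be excluded.

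The room for selective choice also matters less here than in a confirmatory trial. These are secondary outcomes, and section 7.1 disclaims any aim of evaluating efficacy.

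What the reply does not meet is that part 1 states no responder split for the CDRS or C-GAS, part 3 gives its percentages without one, and part 1 specifies a window that includes the phase on which subjects were selected.

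**Conclusion.** The point holds as a modest correction. The synopsis splits by groups that the supplied text does not define. Section 7.2 part 1 can be run, but it states no responder/partial-responder split, includes the acute phase, and puts a safety endpoint where the endpoint list and Hypothesis 6 call for social functioning. So neither statement of the main clinical analysis matches the two hypotheses in their own populations.

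The size is one scale of three, one undefined grouping and one mismatched window, all on secondary outcomes. The feasibility and acceptability endpoint is untouched. The conclusion assumes that the missing figure does not define the groups and that no other document supplies their definition.

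**What to change.** Use the same text in synopsis item 3 and section 7.2 part 1:

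- Estimate change from continuation entry (week 16) through weeks 24 and 32 in CDRS-R, SAS-SR and C-GAS, with 95% confidence intervals, using the repeated-measures or mixed model already planned.
- Report it separately for acute-phase responders (Hypothesis 5) and partial responders (Hypothesis 6). For responders, add CGI response status and the relapse percentage already in part 3.
- Report the C-SSRS with the safety endpoints.
- If decision-point groups from the linked acute study are intended, define them, name their source and keep them as an exploratory split. Otherwise delete the term.

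The cost is wording, provided the linked study's week 16 assessment includes these three scales. Section 3.1 shows an assessment at that week but does not itemise its measures, so this should be confirmed.

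The statistical price is wider intervals. For a mean change with complete data, the 95% half-width is t × SD / √n. With all 30 pooled it is 2.045/√30 = 0.37 SD. The split is not stated, so as an assumed range: n = 20 gives 2.093/√20 = 0.47 SD, n = 15 gives 2.145/√15 = 0.55 SD, and n = 10 gives 2.262/√10 = 0.72 SD. That is acceptable for a pilot that aims to estimate rather than to test.

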1.1 Background

Adolescent depression is a prevalent and debilitating disorder that places youth at risk for suicidality, other psychiatric diagnoses, and significant psychosocial impairment both during adolescence and into adulthood.^{1,2} Research on the treatment of adolescent depression has dramatically increased over the past two decades. Two psychotherapies meet the American Psychological Association's criteria for "well-established" treatments (interpersonal psychotherapy and cognitive behavioral therapy).³ Fluoxetine, paroxetine, sertraline, and escitalopram also have demonstrated efficacy as pharmacological treatments.⁴⁻⁸ While the progress in this area has been substantial, the overwhelming majority of treatment studies have focused on the acute phase of treatment, that is, the phase of treatment focused on initial clinical response and remission of symptoms.⁹ However, among the acute treatment studies that have reported long-term follow-up data, 25-50% of the adolescents in these studies experienced a depressive relapse following the completion of treatment.¹⁰⁻¹³

The American Academy of Child and Adolescent Psychiatry Practice Parameter for the treatment of depression recommends providing continuation treatment following the symptom remission achieved during the acute phase of treatment.¹⁴ The goals of continuation treatment are to consolidate the acute phase treatment response and avoid relapse. Research on continuation phase treatment for adolescent depression is extremely limited, and as a consequence, this Practice Parameter was based primarily on adult treatment studies and clinical consensus.¹⁴ The handful of studies with adolescents that have examined postacute treatment have found that continuation treatment is associated with a decreased risk of relapse,^{11,15,16} and can facilitate further symptom reduction in adolescents who were partial responders to acute phase treatment.^{11,17}

One of the primary risk factors for relapse in youth is interpersonal conflict, particularly within the adolescent's family.^{10,18} As a consequence, it has been recommended that continuation treatments for adolescent depression focus not only on the depressive symptoms, but on the family conflict and relationship problems that may trigger a relapse.¹⁹ Interpersonal Psychotherapy for Depressed Adolescents (IPT-A)²⁰ is a natural treatment modality for targeting both depressive symptoms and interpersonal risk factors. IPT-A is an evidence-based psychotherapy that aims to reduce adolescents' depressive symptoms by helping them improve their relationships and interpersonal interactions.²¹⁻²³ Of note, our group found that the benefits of IPT-A are particularly strong for adolescents who report high levels of conflict with their mothers.²⁴ This finding is significant in light of previous studies that have found that perceived parent-adolescent conflict predicted a poorer treatment response.^{10,25} A continuation

CONFIDENTIAL

version of IPT-A has not yet been studied in a clinical trial. However, IPT as a continuation treatment for adult depression has been investigated, and the results indicated that patients had significantly lower relapse rates.^{26,27} In addition, continuation IPT has been found to decrease the impact of negative life events in provoking relapse.²⁸ This suggests that continuation versions of IPT-A may be useful for preventing the relapse of adolescent depression, as well.

The primary aim of this study is to develop and assess the feasibility and acceptability of a personalized approach to delivering continuation treatment for adolescent depression. The development of evidence-based guidelines for personalizing treatments has been identified as a public health priority²⁹ (NIMH Strategic Plan, 2008, Strategy 3.2: Expand and deepen the focus to personalize intervention research). Personalized interventions, also known as adaptive treatment strategies, provide empirically-derived guidelines or decision rules that recommend when, how, and for whom treatment should be changed to meet the needs of individual patients.^{30,31} Adaptive treatment strategies can, for example, operationalize for patients who are responding to a given treatment, what kind of treatment plan to follow for the continuation phase of treatment. These decision rules are based on patient characteristics and outcomes collected during the treatment process, such as patient response and adherence.

We are currently conducting a pilot study of a personalized approach to acute phase treatment for adolescent depression ([name], PI, K23MH090216). Adolescents begin treatment with IPT-A and may have their treatment augmented either with an increased number of therapy sessions or the addition of fluoxetine if they are showing an insufficient response to treatment. The proposed study would examine the feasibility and acceptability of extending the adaptive treatment strategy into the continuation phase of treatment. There is a clear need for the development and empirical examination of continuation treatments for depression in youth. Given the significant impact that adolescent depression has on both adolescent and adult development and functioning, a continuation treatment that achieves a sustained remission and prevents relapse could have considerable public health significance.

1.2 Investigational Agent

PROZAC® (fluoxetine capsules, USP) is a selective serotonin reuptake inhibitor for oral administration. It is also marketed for the treatment of premenstrual dysphoric disorder (Sarafem®, fluoxetine hydrochloride). It is designated (\pm)-N-methyl-3-phenyl-3-[(α,α,α -trifluoro-*p*-tolyl)oxy]propylamine hydrochloride and has the empirical formula of C₁₇H₁₈F₃NO•HCl. Its molecular weight is 345.79.

Fluoxetine hydrochloride is a white to off-white crystalline solid with a solubility of 14 mg/mL in water. Each Pulvule® contains fluoxetine hydrochloride equivalent to 10 mg (32.3 μ mol), 20 mg (64.7 μ mol), or 40 mg (129.3 μ mol) of fluoxetine. The Pulvules also contain starch, gelatin, silicone, titanium dioxide, iron oxide, and other inactive ingredients. The 10 and 20 mg Pulvules also contain FD&C Blue No. 1, and the 40 mg Pulvule also contains FD&C Blue No. 1 and FD&C Yellow No. 6.

CONFIDENTIAL

This material is the property of the University of Minnesota. Do not disclose or use except as authorized in writing by the study sponsor

PROZAC Weekly™ capsules, a delayed-release formulation, contain enteric-coated pellets of fluoxetine hydrochloride equivalent to 90 mg (291 μmol) of fluoxetine. The capsules also contain D&C Yellow No. 10, FD&C Blue No. 2, gelatin, hypromellose, hypromellose acetate succinate, sodium lauryl sulfate, sucrose, sugar spheres, talc, titanium dioxide, triethyl citrate, and other inactive ingredients.

Although the exact mechanism of PROZAC is unknown, it is presumed to be linked to its inhibition of CNS neuronal uptake of serotonin. Studies at clinically relevant doses in man have demonstrated that fluoxetine blocks the uptake of serotonin into human platelets. Studies in animals also suggest that fluoxetine is a much more potent uptake inhibitor of serotonin than of norepinephrine. Antagonism of muscarinic, histaminergic, and α1-adrenergic receptors has been hypothesized to be associated with various anticholinergic, sedative, and cardiovascular effects of classical tricyclic antidepressant (TCA) drugs. Fluoxetine binds to these and other membrane receptors from brain tissue much less potently in vitro than do the tricyclic drugs.

Systemic Bioavailability — In man, following a single oral 40 mg dose, peak plasma concentrations of fluoxetine from 15 to 55 ng/mL are observed after 6 to 8 hours. The Pulvule and PROZAC Weekly capsule dosage forms of fluoxetine are bioequivalent. Food does not appear to affect the systemic bioavailability of fluoxetine, although it may delay its absorption by 1 to 2 hours, which is probably not clinically significant. Thus, fluoxetine may be administered with or without food. PROZAC Weekly capsules, a delayed-release formulation, contain enteric-coated pellets that resist dissolution until reaching a segment of the gastrointestinal tract where the pH exceeds 5.5. The enteric coating delays the onset of absorption of fluoxetine 1 to 2 hours relative to the immediate-release formulations. OCHCH2CH2NHCH3• HCIF3C21

Weekly Dosing — Administration of PROZAC Weekly once weekly results in increased fluctuation between peak and trough concentrations of fluoxetine and norfluoxetine compared with once-daily dosing [for fluoxetine: 24% (daily) to 164% (weekly) and for norfluoxetine: 17% (daily) to 43% (weekly)]. Plasma concentrations may not necessarily be predictive of clinical response. Peak concentrations from once-weekly doses of PROZAC Weekly capsules of fluoxetine are in the range of the average concentration for 20 mg once-daily dosing. Average trough concentrations are 76% lower for fluoxetine and 47% lower for norfluoxetine than the concentrations maintained by 20 mg once-daily dosing. Average steady-state concentrations of either once-daily or once-weekly dosing are in relative proportion to the total dose administered. Average steady-state fluoxetine concentrations are approximately 50% lower following the once-weekly regimen compared with the once-daily regimen. C_{max} for fluoxetine following the 90 mg dose was approximately 1.7-fold higher than the C_{max} value for the established 20 mg once-daily regimen following transition the next day to the once-weekly regimen. In contrast, when the first 90 mg once-weekly dose and the last 20 mg once-daily dose were separated by 1 week, C_{max} values were similar. Also, there was a transient increase in the average steady-state concentrations of fluoxetine observed following transition the next day to the once-weekly regimen. From a pharmacokinetic

CONFIDENTIAL

perspective, it may be better to separate the first 90 mg weekly dose and the last 20 mg once-daily dose by 1 week [see Dosage and Administration (2.1)].

Daily Dosing -- Adult — The efficacy of PROZAC was studied in 5- and 6-week placebo-controlled trials with depressed adult and geriatric outpatients (≥ 18 years of age) whose diagnoses corresponded most closely to the DSM-III (currently DSM-IV) category of Major Depressive Disorder. PROZAC was shown to be significantly more effective than placebo as measured by the Hamilton Depression Rating Scale (HAM-D). PROZAC was also significantly more effective than placebo on the HAM-D subscores for depressed mood, sleep disturbance, and the anxiety subfactor.

Two 6-week controlled studies (N=671, randomized) comparing PROZAC 20 mg and placebo have shown PROZAC 20 mg daily to be effective in the treatment of elderly patients (≥ 60 years of age) with Major Depressive Disorder. In these studies, PROZAC produced a significantly higher rate of response and remission as defined, respectively, by a 50% decrease in the HAM-D score and a total endpoint HAM-D score of ≤ 8 . PROZAC was well tolerated and the rate of treatment discontinuations due to adverse reactions did not differ between PROZAC (12%) and placebo (9%).

A study was conducted involving depressed outpatients who had responded (modified HAMD-17 score of ≤ 7 during each of the last 3 weeks of open-label treatment and absence of Major Depressive Disorder by DSM-III-R criteria) by the end of an initial 12-week open-treatment phase on PROZAC 20 mg/day. These patients (N=298) were randomized to continuation on double-blind 23 PROZAC 20 mg/day or placebo. At 38 weeks (50 weeks total), a statistically significantly lower relapse rate (defined as symptoms sufficient to meet a diagnosis of Major Depressive Disorder for 2 weeks or a modified HAMD-17 score of ≥ 14 for 3 weeks) was observed for patients taking PROZAC compared with those on placebo.

Pediatric (children and adolescents) — The efficacy of PROZAC 20 mg/day in children and adolescents (N=315 randomized; 170 children ages 8 to < 13 , 145 adolescents ages 13 to ≤ 18) was studied in two 8- to 9-week placebo-controlled clinical trials in depressed outpatients whose diagnoses corresponded most closely to the DSM-III-R or DSM-IV category of Major Depressive Disorder.

In both studies independently, PROZAC produced a statistically significantly greater mean change on the Childhood Depression Rating Scale-Revised (CDRS-R) total score from baseline to endpoint than did placebo. Subgroup analyses on the CDRS-R total score did not suggest any differential responsiveness on the basis of age or gender.

Weekly dosing for Maintenance/Continuation Treatment--A longer-term study was conducted involving adult outpatients meeting DSM-IV criteria for Major Depressive Disorder who had responded (defined as having a modified HAMD-17 score of ≤ 9 , a CGI-Severity rating of ≤ 2 , and no longer meeting criteria for Major Depressive Disorder) for 3 consecutive weeks at the end of 13 weeks of open-label treatment with PROZAC 20 mg once daily. These patients were randomized to double-blind, once-weekly continuation treatment with PROZAC Weekly, PROZAC 20 mg once daily, or placebo.

CONFIDENTIAL

PROZAC Weekly once weekly and PROZAC 20 mg once daily demonstrated superior efficacy (having a significantly longer time to relapse of depressive symptoms) compared with placebo for a period of 25 weeks. However, the equivalence of these 2 treatments during continuation therapy has not been established.

----- **INDICATIONS AND USAGE** -----

PROZAC® (fluoxetine hydrochloride) is a selective serotonin reuptake inhibitor indicated for:

- Acute and maintenance treatment of Major Depressive Disorder (MDD) in adult and pediatric patients aged 8 to 18 years
- Acute and maintenance treatment of Obsessive Compulsive Disorder (OCD) in adult and pediatric patients aged 7 to 17 years
- Acute and maintenance treatment of Bulimia Nervosa in adult patients
- Acute treatment of Panic Disorder, with or without agoraphobia, in adult patients

----- DOSAGE AND ADMINISTRATION ----- Indication	Adult	Pediatric
MDD (2.1)	20 mg/day in am (initial dose)	10 to 20 mg/day (initial dose)
Depressive Episodes Associated with Bipolar I Disorder (2.5)	Oral in combination with olanzapine: 5 mg of oral olanzapine and 20 mg of fluoxetine once daily (initial dose)	-
Treatment Resistant Depression (2.6)	Oral in combination with olanzapine: 5 mg of oral olanzapine and 20 mg of fluoxetine once daily (initial dose)	-

----- **DOSAGE FORMS AND STRENGTHS** -----

CONFIDENTIAL

This material is the property of the University of Minnesota. Do not disclose or use except as authorized in writing by the study sponsor

- Pulvules: 10 mg, 20 mg, 40 mg (3)
- Weekly capsules: 90 mg (3)

